#### Full Analysis Set (FAS)

The FAS analysis population is not HPV type-specific. The FAS population includes subjects who received at least 1 dose of 9-valent HPV L1 VLP vaccine and had at least 1 follow-up visit during the long-term follow-up study.

Only FAS population-eligible subjects who are at least 16 years of age and have at least one follow-up visit with PCR data will contribute to assessments of effectiveness in the FAS.

#### 3.5.5 Statistical Methods

#### **3.5.5.1 Statistical Methods for Immunogenicity Analyses**

Immunogenicity summaries are planned to occur in Protocol 002-20 at three time points, to include follow-up data through Month 72, Month 96, and Month 126. Anti-HPV responses to each of the 9 vaccine HPV types will be summarized for both cLIA and IgG assay by gender and age at enrollment as GMTs and seropositivity rates, with associated 95 % confidence intervals, at each time point at which serology samples were collected, regardless of study visit windows.

In addition, exploratory analyses regarding the kinetics and persistence of antibody response may be conducted, with particular interest in the effect of age at first vaccination on duration of anti-HPV levels. Modeling techniques may be used to study the relationship between anti-HPV persistence and factors such as time since vaccination, age at vaccination, age at sexual debut, and GMT at 1 month post-dose 3.

#### **3.5.5.2 Statistical Methods for Safety Analyses**

Listings and narratives of subjects who experienced serious adverse experiences will be provided by vaccination group.

A summary of pregnancy outcomes will be provided. A summary of counts and percentages (relative to the total number infants/fetuses with known outcomes) of specific pregnancy outcomes will be provided.

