### 1.5 SAMPLE

All subjects who were enrolled in Protocol V503-002 between the ages of 9 and 15 years and received 3 doses of 9-valent HPV L1 VLP vaccine are eligible for enrollment in this extension. Protocol V503-002 enrolled 2604 subjects between the ages of 9 to 15 years. Among them, 2552 subjects received 3 doses of 9-valent HPV L1 VLP vaccine.

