#### 2.1.3 Safety Objective

**Objective:** To describe the incidence of serious adverse experiences (deemed to be vaccine-related or procedure-related) in subjects who received 9-valent HPV L1 VLP vaccine at 9 to 15 years of age.

Effectiveness, immunogenicity, and safety summaries will be provided for estimation purposes only. Thus, there are no formal hypotheses for the study extension.

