### 2.7.3 Safety analysis

All subjects who received at least one dose of 9-valent HPV L1 VLP vaccine and have long-term study follow-up data will be included in the safety summaries. Listings of serious adverse experiences and deaths, and a pregnancy summary will be provided.

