#### **3.5.3.2 Safety Endpoints**

Safety endpoints are vaccine- or study procedure-related serious adverse experiences, deaths, and pregnancy- and infant-related outcomes.

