#### **3.5.4.2 Safety Analysis Populations**

All subjects who received at least 1 study vaccination and have follow-up data will be included in the safety summaries.

76

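### The safety objective is to describe the incidence of related SAEs, but the analysis sections specify only listings and narratives for SAEs, with no incidence statistic or interval

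*Combined protocol and SAP*

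**What the plan says.** The safety objective in Section 2.1.3 is "To describe the incidence of serious adverse experiences (deemed to be vaccine-related or procedure-related") in subjects vaccinated at 9 to 15 years of age. The same section adds: "Effectiveness, immunogenicity, and safety summaries will be provided for estimation purposes only".

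Section 3.5.3.2 names the endpoints: "Safety endpoints are vaccine- or study procedure-related serious adverse experiences, deaths, and pregnancy- and infant-related outcomes". Section 3.5.4.2 defines who is counted: "All subjects who received at least 1 study vaccination and have follow-up data will be included in the safety summaries".

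Two places give the analysis:
- Section 2.7.3: "Listings of serious adverse experiences and deaths, and a pregnancy summary will be provided".
- Section 3.5.5.2: "Listings and narratives of subjects who experienced serious adverse experiences will be provided by vaccination group". For pregnancies, but not for SAEs, it goes on to plan numbers: "A summary of counts and percentages (relative to the total number infants/fetuses with known outcomes) of specific pregnancy outcomes will be provided".

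Section 3.5 states that this section is the analysis plan and that no separate SAP will follow.

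**The concern.** An incidence is a count over a denominator, or over person-time. For SAEs the methods sections specify neither, and no interval, although the document says its safety summaries serve estimation. Followed to the letter, the plan meets its safety objective only if someone adds a calculation that it does not contain.

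This matters most when counts are small. Section 2.6 restricts collection to deaths and to SAEs judged related to vaccine or procedure, so few or no related events is plausible, although the documents give no expected rate. An empty listing does not say what rate has been excluded. That depends on how many subjects enrolled and how long they were followed, and the planned SAE output states neither.

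**Working it through.** **The sections side by side**

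| Outcome | Statistic specified | Where |
|---|---|---|
| GMTs, seropositivity | Estimates with 95% intervals | 3.5.5.1 |
| Effectiveness incidence | Rate per 100 person-years, exact Poisson 95% interval | 3.5.5.3 |
| Pregnancy outcomes | Counts and percentages, denominator stated | 3.5.5.2 |
| SAEs | Listings and narratives | 2.7.3, 3.5.5.2 |

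The plan quantifies every other outcome in this table. The document gives no SAE rate or precision, so there is no stated figure to reproduce.

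**What the missing statistic would show**

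Inputs:
- Maximum enrolment is 2552, because Section 1.5 reports that "2552 subjects received 3 doses of 9-valent HPV L1 VLP vaccine" and Section 2.2 requires three doses. Actual enrolment in the extension is not given; 1500 and 1000 are assumptions.
- Follow-up runs from Month 42 to Month 126. By the visit labels this is (126 − 42)/12 = 7.0 years. Section 2.4.1 says about 7.5 years, which matches a start at Month 36: (126 − 36)/12 = 7.5.
- Person-years assume no dropout.

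*Proportion, 0 events.* Exact two-sided 95% upper limit = 1 − 0.025^(1/N):
- N = 2552: 0.00144, or 0.14%
- N = 1500: 0.00246, or 0.25%
- N = 1000: 0.00368, or 0.37%

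*Proportion, a few events, N = 2552* (Clopper-Pearson):
- 1 subject: 0.039% (0.001% to 0.218%)
- 2 subjects: 0.078% (0.009% to 0.283%)
- 5 subjects: 0.196% (0.064% to 0.457%)

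*Rate, 0 events.* Exact Poisson upper limit = −ln(0.025)/person-years = 3.689/person-years:
- 2552 × 7.0 = 17,864 person-years: 0.0207 per 100
- 2552 × 7.5 = 19,140 person-years: 0.0193 per 100
- 1000 × 7.0 = 7000 person-years: 0.0527 per 100

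Across the assumed enrolments the zero-event limit changes by a factor of about 2.5 (0.37/0.14 = 2.6 from the rounded figures). The choice between 7.0 and 7.5 years changes the rate limit by about 7% (7.5/7.0 = 1.07).

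**The case against.** The strongest reply is that this is a wording mismatch in a descriptive study. There are no hypotheses, the objective is only to describe, and the safety population is defined. A complete listing together with the size of that population gives a crude proportion, from which a reader could derive an exact bound. This much stands: the documents do not support saying that no incidence could be obtained. They support saying that none is specified. It is also right that the safety section is not wholly unquantified, since pregnancy outcomes get counts and percentages.

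Two stronger readings are tempting and do not hold.

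- *The whole safety set is the wrong base for procedure-related SAEs, because genital examination and sampling start at 16.* Section 3.2.2.8 schedules blood draws for every subject, including those under 16, so all followed subjects are due study procedures. The age limit also expires: a subject enrolled at 9 reaches 16 by about Month (16 − 9) × 12 = 84. Nothing in the documents shows that most procedure-related SAEs would come from genital procedures.
- *The vaccination group does not exist.* Section 3.5.1 says all participants received the 9-valent vaccine, which rules out a comparator. Section 3.2.2.3 says subjects were randomized in the base study and keep their allocation numbers, and the title refers to manufacturing consistency. The term is undefined here, but the documents do not show that it is empty.

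The reply that the absence of hypotheses makes an interval unnecessary does not stand: the plan states estimation as its purpose and gives intervals for its other descriptive results.

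**Conclusion.** The concern holds as a mismatch between objective and method. Section 2.1.3 asks for the incidence of related SAEs; Sections 2.7.3 and 3.5.5.2 specify no incidence statistic or interval for them, and no later plan is due to supply one.

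The practical loss is the bound when events are rare: with 0 events, about 0.14% at full enrolment of 2552, and 0.25% or 0.37% at 1500 or 1000. These figures rest on assumed enrolment and on an assumed count of zero; the document gives neither.

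The consequence is limited. It does not touch the primary immunogenicity objective, the sample size or the interim rule, and a crude proportion could still be worked out from the listing. It is worth correcting because the stated safety objective otherwise has no matching analysis.

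**What to change.** In Sections 3.5.5.2 and 2.7.3:

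1. Add the number and percent of safety-population subjects with (a) a vaccine-related SAE, (b) a procedure-related SAE and (c) death, each with an exact 95% confidence interval. Deaths are outside the wording of the objective but are a named safety endpoint in Section 3.5.3.2.
2. Add a rate per 100 person-years of extension follow-up, with the exact Poisson interval already named in Section 3.5.5.3. State when person-time starts, since the visit labels and the duration in Section 2.4.1 differ by half a year.
3. Define the vaccination group for this extension, in which all participants received the 9-valent vaccine, or remove the phrase.
4. Keep the whole safety population as the base for procedure-related SAEs. At most, add a supplementary split for genital procedures at age 16 and over.

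Listings and narratives stay as planned. The cost is one small table at each of the three analyses (Months 72, 96 and 126), with no new data collection.

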# 3.4.4 Reporting of Pregnancy/Breastfeeding Events to the SPONSOR

Although not considered an adverse experience, it is the responsibility of the investigators or their designees to report any pregnancy in a subject (spontaneously reported to them or detected by urine or serum pregnancy test per protocol).

All randomized subjects who receive study vaccine, including discontinued subjects who agree to provide further information, must be followed to the completion/termination of the pregnancy. In addition, if the pregnancy continues to term, the outcome (health of the infant) must be reported.

Infant serious adverse experiences (SAEs) for all infants born to subjects who received study vaccine must be reported to the SPONSOR.

The reporting of pregnancy and infant SAE events must be reported within 24 hours to the SPONSOR either by electronic media or paper. Refer to Data Entry Guidelines (DEGs) for instructions for what information must be reported.

68

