### 3.5.1 Responsibility for Analyses/In-House Blinding

The statistical analysis of the data obtained from this study will be the responsibility of the Clinical Biostatistics department of the SPONSOR.

This extension of Protocol 002 will not be blinded, because all participants will have received 9-valent HPV L1 VLP vaccine. Freezes of the clinical database will be executed for each of the interim analyses at Months 72 and 96 and at end-of-study. Prior to each data freeze, the clinical data will be reviewed, cleaned, and screened to ensure accuracy and completeness following the SPONSOR's Global Development Processes (GDP) relating to Data Management. The data will be reviewed and errors will be corrected and protocol violations have been reviewed prior to freezing the clinical database for immunogenicity, safety, and effectiveness analyses.

The first analysis conducted under Protocol 002-20 is planned to take place at Month 72. During this interim analysis, safety, immunogenicity, and effectiveness data will be analyzed and feasibility of continuing the study through Month 126 will be assessed. If study continues beyond Month 72, additional analyses of safety, immunogenicity and effectiveness are planned to include data through Month 96 and Month 126.

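### With percentages taken only over known pregnancy outcomes, an interim table will overstate the share of losses relative to what the same reported pregnancies will finally show; a gestation cut-off and a count of ongoing pregnancies would remove this (minor).

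*Combined protocol and SAP*

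**What the plan says.** Section 3.5.3.2 makes pregnancy results a safety endpoint: "Safety endpoints are vaccine- or study procedure-related serious adverse experiences, deaths, and pregnancy- and infant-related outcomes". Section 2.7.3 promises the output: "Listings of serious adverse experiences and deaths, and a pregnancy summary will be provided". Section 3.5.5.2 sets the denominator: "A summary of counts and percentages (relative to the total number infants/fetuses with known outcomes) of specific pregnancy outcomes will be provided". The unit is the infant or fetus, and counts are promised as well as percentages.

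On timing, Section 3.5.1 says: "Freezes of the clinical database will be executed for each of the interim analyses at Months 72 and 96 and at end-of-study". Of Month 72 it says: "During this interim analysis, safety, immunogenicity, and effectiveness data will be analyzed". If the study continues, "additional analyses of safety, immunogenicity and effectiveness are planned to include data through Month 96 and Month 126". Neither 2.7.3 nor 3.5.5.2 names a time point for the pregnancy table, so its production at the interims is inferred from 3.5.1 and 3.5.3.2 together.

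On follow-up, Section 3.4.4 says that pregnancies in vaccinated subjects "must be followed to the completion/termination of the pregnancy". A pregnancy still open at one freeze should therefore appear with its outcome at a later one. Nothing delays a freeze until open pregnancies resolve, sets a conception cut-off for the percentages, or says how open pregnancies are displayed.

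**The concern.** The two kinds of outcome become known at different speeds. A loss is usually known within a few months of conception, while a birth takes about nine. Of the pregnancies begun in the last months before a freeze, some losses are already countable and no term births are. The stated denominator keeps those losses and drops the pregnancies still open, most of which will end in birth. Whether a pregnancy is counted thus depends on the outcome being estimated. This is right truncation.

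All subjects received the vaccine, so no concurrent control group carries the same distortion. A reader of an interim report would see a loss percentage that is too high for the pregnancies reported so far, and that could fall between freezes with no real change.

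**Working it through.** The documents give no pregnancy count, loss rate or timing, so there is no plan figure to reproduce.

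**Inputs from the documents**
- Freezes at Months 72 and 96 and at end of study (3.5.1).
- The extension starts at Month 42 (2.4.1). Accrual time T is therefore 72 − 42 = 30 months and 96 − 42 = 54 months if pregnancies are counted from Month 42, or 72 and 96 months if counted from Day 1. The plan does not say which.

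**Assumptions (not in the documents)**
- True loss proportion p = 15%, varied from 10% to 25%, with losses treated as one class.
- A loss is known 2.5 months after conception (varied from 1.5 to 4), a birth at 9 months.
- All pregnancies are reported, and outcomes are cut at the freeze month.
- The conception rate is flat, grows exponentially at up to g = 0.4 per year, or rises linearly from zero.

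**Formula.** With F(a) the conceptions in the first a months of accrual,

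loss % at freeze = p·F(T − 2.5) / [p·F(T − 2.5) + (1 − p)·F(T − 9)].

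F(a) is proportional to a (flat), to e^(ga/12) − 1 (exponential), or to a² (linear from zero).

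**Month 72, counted from Month 42**
- Flat: 0.15 × 27.5 = 4.125 and 0.85 × 21 = 17.85, so 4.125 / 21.975 = 18.8%.
- g = 0.4: F is 1.501 for losses and 1.014 for births, so 0.225 / (0.225 + 0.862) = 20.7%.
- Linear from zero at Month 42: 0.15 × 27.5² = 113.4 and 0.85 × 21² = 374.9, so 113.4 / 488.3 = 23.2%.

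**All cases, p = 15%**

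| Freeze | Counted from | Flat | g = 0.4 | Linear from zero |
|---|---|---|---|---|
| Month 72 | Month 42 | 18.8% | 20.7% | 23.2% |
| Month 72 | Day 1 | 16.3% | 18.4% | 17.7% |
| Month 96 | Month 42 | 16.8% | 18.8% | 18.8% |
| Month 96 | Day 1 | 15.9% | 18.1% | 16.9% |

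**Sensitivity (Month 72, from Month 42, flat).** A true loss of 10% reads 12.7%, and 25% reads 30.4%. With p = 15%, a loss known at 1.5 months gives 19.3%, and at 4 months 17.9%.

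**Incomplete reporting of losses (flat, from Month 42).** If only half of losses are ever reported, the reported pregnancies will finally show 0.075 / (0.075 + 0.85) = 8.1%.
- Month 72 would show 0.075 × 27.5 / (0.075 × 27.5 + 17.85) = 10.4%.
- Month 96 would show 0.075 × 51.5 / (0.075 × 51.5 + 0.85 × 45) = 9.2%.

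Both are above 8.1% but below the true 15%. The two errors cancel when the captured share of losses is 21/27.5 = 76% at Month 72 or 45/51.5 = 87% at Month 96.

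**With a cut-off.** If only pregnancies begun at least one gestation G before the freeze count, F(T − G) multiplies both outcomes and cancels. The result is p under complete reporting, and 8.1% in the half-reported case. Truncation is removed and under-reporting is not.

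**The case against.** Five points can be made against this.

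- **Net direction.** Under Section 3.4.4 pregnancies are "spontaneously reported to them or detected by urine or serum pregnancy test per protocol". Testing is optional, and visits are six months apart from age 16 and yearly before that. An early loss between visits is more easily missed than a birth. A reader might infer from the mechanism that the interim table overstates the true loss rate. The documents do not support that, since enough under-reporting turns the net error negative. This objection stands against any claim about the true rate. It does not remove the truncation, which acts on whatever is reported.
- **Timing is inferred.** A reader might take the plan to state that the pregnancy table is produced at Months 72 and 96. It does not. That is a fair inference from 3.5.1, not a written rule.
- **Size.** Every magnitude rests on outside assumptions. From Day 1 the shift is about 1 to 3 points. With an assumed 50 to 100 known outcomes, the sampling error of a figure near 18.8% is √(0.188 × 0.812 / n), or about 4 to 5.5 points. This stands. However, subjects enrolled at 9 to 15 years are about 15 to 21 at Month 72, and the base study required no coitarche at entry. A flat conception rate from Day 1, which gives the smallest shift, is thus an unlikely pattern.
- **Later freezes repair it.** Pregnancies open at an interim do enter later. Counted from Month 42 at a flat rate, Month 126 gives 0.15 × 81.5 / (0.15 × 81.5 + 0.85 × 75) = 16.1%. This largely stands, although a rate still rising would leave more, and the interim reports remain as issued.
- **Nothing depends on it.** Summaries are for estimation only (2.1.3). The table has no comparator, and the rule in 3.5.9 for ending the effectiveness component uses only effectiveness follow-up. This stands and keeps the point minor.

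**Conclusion.** The point holds in a limited form. If the pregnancy table is produced at the interim freezes, as 3.5.1 implies, the known-outcome denominator makes its loss percentage too high relative to what the same reported pregnancies will show when all are resolved. That direction follows from the denominator rule and from losses resolving before births.

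The size does not follow from the documents. Under an assumed 15% true loss and complete reporting, the table would read about 16% to 21% at Month 72 and 16% to 19% at Month 96. The Month 72 upper end is about 23% if conceptions rise linearly from zero at Month 42. The spread reflects the conception pattern and whether counting starts at Day 1 or Month 42.

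A reader might go further and expect a false safety signal or a damaged study conclusion. The plan gives no ground for that: the table is descriptive, it has no reference rate, and no hypothesis or decision rule uses it. Severity is minor.

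**What to change.** Add to Section 3.5.5.2: *At each database freeze, percentages of pregnancy outcomes will be calculated among infants/fetuses with known outcomes from pregnancies whose LMP or estimated conception date precedes the data cut-off by at least one full gestation (for example, 42 weeks from LMP). Counts for all reported pregnancies will be shown beside them, with ongoing pregnancies and those with unknown or lost-to-follow-up outcomes listed separately.* The same sentence should say at which freezes the table is produced and whether pregnancies are counted from Day 1 or Month 42.

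This keeps the plan's unit, so multiple births are handled as now. It also keeps unknown outcomes out of the denominator, where they would pull every percentage down. It does not correct for unreported early losses.

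The cost is a short text change and a date filter, with no new visits or data beyond the LMP or due date. Whether either date is on the pregnancy report must be checked, because 3.4.4 leaves its content to the Data Entry Guidelines.

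The downside is fewer pregnancies in the interim percentages. With a 10-month cut-off, counting from Month 42:
- Month 72, flat rate: 20/30 = 67% of pregnancies qualify, against 0.15 × 27.5/30 + 0.85 × 21/30 = 73% with known outcomes.
- Month 72, linear rise from zero: (20/30)² = 44%, against 0.15 × (27.5/30)² + 0.85 × (21/30)² = 54%.
- Month 96, flat rate: 44/54 = 81% qualify.

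The full counts stay on display throughout.

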#### **3.5.5.3 Statistical Methods for Effectiveness Analyses**

Subjects who meet the criteria to be considered cases of vaccine type HPV-related persistent infection and/or disease, but who have evidence of HPV exposure or infection (i.e., seropositivity to the respective HPV type(s) pre-vaccination or evidence of sexual activity prior to the completion of their vaccination series), or who do not complete their three doses of 9-valent HPV L1 VLP vaccine within one year, will not be considered breakthrough cases (i.e., vaccine failures). Such cases will be summarized separately in a manner similar to breakthrough cases, with all relevant factors such as baseline demographics and immunogenicity profiles over time characterized; however, these cases will not be included in the primary summary of effectiveness endpoints.

78

At the time of the interim analysis (Month 72), summaries of the incidence of HPV 6, 11, 16, 18-related persistent infection for a duration of  $\geq 6$  months (within  $\pm 1$  month windows) and cervical, vulvar, vaginal, perineal, perinanal, and penile intraepithelial preinvasive and invasive disease, and external genital lesions will be provided, separately for males and females. Similar summaries of the incidence rates of HPV 6, 11, 16, 18, 31, 33, 45, 52, and 58-related persistent infection for a duration of  $\geq 6$  months (within  $\pm 1$  month windows) and disease will be provided to include follow-up data through Month 96 and Month 126.

The confidence intervals around the point estimate of the incidence rates per 100 personyears are exact Poisson distribution-based nominal 95% confidence intervals.

Summaries will be provided by gender. At each analysis time point, the cumulative incidence rate for effectiveness endpoints will be computed, along with the associated 95% confidence interval. In addition, exploratory analyses will be conducted to characterize subjects who become cases of persistent infection or disease endpoints in the long-term effectiveness follow-up period. Baseline demographic characteristics, prevaccination anti-HPV serology status, and post-vaccination immunogenicity profiles will be considered. Time-to-event plots will also be provided by gender if >5 cases are observed in the respective group(s).

Any comparisons of the incidence rates of effectiveness endpoints between Protocol V503-002 and Protocol V503-001 will be descriptive and no formal statistical comparisons will be made. Merck is undertaking other studies to evaluate the long-term effectiveness of 9-valent HPV L1 VLP vaccine.

Incidence rates of the same endpoints described above will be summarized for additional HPV types for which PCR testing is planned in this study (35, 39, 51, 56, and 59). These data, when available, will provide information related to incidence of non-vaccine type HPV in this population and potential cross-protection against these additional HPV types.

An additional analysis of persistent infection for a duration of 12 months (within  $\pm 1$  month windows) or more will be conducted.

